2.4 Study rationale

Immunization Schedule: The target population of this clinical trial is children aged 6-35 months, with an immunization schedule of 2 doses (28 days apart), consistent with the approved trivalent or quadrivalent influenza vaccines currently on the market.

Vaccination Dose: The vaccination doses in this clinical trial include the 0.25ml dose (containing 7.5 μ g of hemagglutinin for each strain) and the 0.5ml dose (containing 15 μ g of hemagglutinin for each strain). Among them, the 0.25ml influenza vaccine has been used in the 6-35 months age group for over 30 years. Initially, half-dose antigen influenza vaccines were developed to reduce the risk of fever convulsions that might be caused by whole-virus influenza vaccines ^[23]. However, several recent studies have shown that children under 3 years old can receive full-dose vaccines to enhance immunogenicity without increasing the severity or incidence of fever or other adverse reactions ^[24-26]. In the United States, the 0.5ml dose of QIV was first approved for use in children aged 6-35 months in 2016. Currently, multiple domestic manufacturers are also conducting clinical trials on both 0.25ml and 0.5ml doses vaccines in this population.

Control Selection: In this clinical trial, two 0.25ml trivalent influenza vaccines (TIVs, Anflu®) marketed by Sinovac were selected as the control vaccines. Anflu® has been marketed and used in China for 20 years, with previous study results showing good protective efficacy, immunogenicity, and safety. The immunogenicity results would be comparable due to the same strains and manufacturing process between test and control vaccines. Additionally, relevant studies have shown that some indicators of immune responses to the two B serotypes in quadrivalent influenza vaccines may be lower than those in trivalent influenza vaccines. For example, in a clinical study of quadrivalent influenza vaccines in the 6-35 months age group, the geometric mean titers (GMT) of HI antibodies against the BV serotype at 28 days after full immunization were 64.0 in the 0.25ml quadrivalent influenza vaccine group and 91.3 in the trivalent influenza vaccine (containing BV) group; the GMTs of HI antibodies against the BY serotype were 96.6 in the 0.25ml quadrivalent influenza vaccine group and 106 in the trivalent influenza vaccine (containing BY) group ^[27].

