4.1 Overall Design

This study is a multi-center, randomized, double-blind, controlled trial design. The control vaccines will be Anflu®, trivalent influenza virus split vaccines already marketed by Sinovac (including type B Victoria or type B Yamagata). This trial is a multi-center, randomized, double-blinded, and positive-controlled design. The control vaccine is Anflu®, two 0.25mL-dose trivalent influenza virus split vaccines (TIVs, containing a B Victoria lineage or B Yamagata lineage) marketed by Sinovac. This trial will be conducted on children aged 6 to 35 months with the informed consent of their guardians. A total of 3,300 participants are planned to be recruited and randomly assigned to 4 groups in a ratio of 2:2:1:1, namely the 0.25mL-dose QIV group, 0.5ml-dose QIV group, TIV-BV group, and TIV-BY group. All participants receive 2 doses of the test vaccine or control vaccine according to the 0, 28-day immunization schedule. Among them, subjects aged 6 to 11 months (before their first birthday) will receive intramuscular injections in the anterolateral thigh, and those aged 12 to 35 months will receive intramuscular injections in the deltoid muscle of the upper arm.

Table 4.1.1 Phase III Study Design

Group	Vaccine	Sample Size	Immunization schedule (days)	Antibody test blood collection point (day)
Test Group 1	Influenza Vaccine (Split Virion), Inactivated, Quadrivalent (0.25mL)	1100	0, 28	0, 56
Test Group 2	Influenza Vaccine (Split Virion), Inactivated, Quadrivalent (0.5mL)	1100	0, 28	0, 56
Control Group 1	Influenza Vaccine (Split Virion), Inactivated, Anflu (0.25mL, including BV)	550	0, 28	0, 56
Control Group 2	Influenza Vaccine (Split Virion), Inactivated, Anflu (0.25mL, including BY)	550	0, 28	0, 56
Total	\	3300	\	\

Safety evaluation: All participants are observed for immediate reactions for 30 minutes after each dose, solicited systemic and local adverse events within 0-7 days, and unsolicited adverse events within 0-28 days after each dose. Additionally, monitoring of serious adverse events (SAEs) and adverse events of special interest (AESIs) is conducted from the first dose administration to 6 months after the second vaccination to evaluate the safety.

Immunogenicity evaluation: About 2 to 3mL of venous blood is collected from each subject before vaccination and 28 days after full-course vaccination, respectively, and then the serum is isolated and

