4.3 Sample Size

This trial requires the test group: ① the non-inferiority comparison with the control groups is established and the next statistical test is carried out; ② when the absolute criteria of SCR and SPR are achieved, the trial can be considered as successful and a positive conclusion can be drawn for the test group. In this trial, when evaluating between the test group 1 (0.25-mL QIV) and test group 2 (0.5mL-QIV), the strategy of sequential test is adopted. First, test group 2 is evaluated. If the positive conclusion of test group 2 is established, test group 1 is further evaluated. Therefore, class I error correction is no longer carried out. The sample size of phase III clinical trials is estimated first by non-inferiority design, namely the QIV group is non-inferior to the TIV group. The primary endpoints of this study include two indicators: SCR and GMT. Only when the SCR and GMT of four serotypes in test group are non-inferior to the control vaccine, the investigational vaccine is considered to be non-inferior to the control vaccine. The total power is 80%, the type II error is 0.2. Based on the different sample size requirements of the two indicators, the type II error is allocated, with 0.16 for SCR comparison and 0.04 for GMT comparison.

(1) Calculation of sample size with the SCR as the indicator:

According to the results of the previous Anflu phase IV clinical trial and other literature, the SCR of the types contained in the vaccine 28 days after vaccination is over 65%, which is used as the reference proportion to estimate the sample size. The test level is taken as one-sided $\alpha=0.025$, the power of non-inferiority comparison for the SCR of a serotype is taken as $1-\beta1/4=1-0.16/4=96\%$, and the non-inferiority threshold Δ is taken as -10%. When comparing the non-inferiority of BY or BV strain, NT:NC=2:1, and PASS software is used to calculate the sample size, the test group needs 914 samples and the control group needs 457 samples. When the non-inferiority test of H1N1 or H3N2 strain is carried out, two control groups are pooled. The sample size ratio of the test group and the pooled control group is 1:1, and the test group and the pooled control group need 625 participants.

(2) Calculation of sample size with the GMT as the indicator:

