Meanwhile, the Kaplan-Meier method will be used to calculate the median duration of AEs and their 95% confidence intervals in each group, respectively (using the Brookmeyer & Crowley method of log-log transformation), and the log-rank test will be used to statistically test the differences between groups. The AEs after each dose of vaccination will be statistically analyzed respectively. The analysis of AEs for each dose will be based on the safety datasets of each dose.

Present the forest plots to compare the differences in the incidence rates of AEs between the two groups (test group 1 - control group 1), (test group 1 - control group 2), (test group 2 - control group 1), and (test group 2 - control group 1) according to the top ten preferred terms for incidence rates in the vaccine group.

When calculating the incidence of AEs, if the same AE occurs multiple times in the same subject, it is recorded as one occurrence. When calculating the number of events of AEs, if the same subject experiences the same AE multiple times, it is recorded multiple times. When analyzing the severity and correlation to the investigational vaccine of AEs, if the same AE occurs multiple times in the same subject, the most severe or the most relevant AE to the investigational vaccine should be selected for analysis.

Display the list of AEs related to the investigational vaccine, the list of AEs unrelated to the investigational vaccine, the list of AEs leading to drop out, and the list of Grade 3 or above AEs.

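### SAP 6.9.1 lists one adverse-event contrast twice and so leaves out 0.5 mL QIV versus TIV-BY; separately, no between-dose adverse-event difference is planned

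*SAP*

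**What the plan says.** In SAP 6.9.1 the instruction for the figures begins "Present the forest plots to compare the differences in the incidence rates of AEs between the two groups". The contrasts follow: "test group 1 - control group 1), (test group 1 - control group 2), (test group 2 - control group" 1), and then the final pair. The list ends "and (test group 2 - control group 1) according to the top ten preferred terms for incidence rates" in the vaccine group.

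The labels are fixed elsewhere in the SAP. Section 4.3 identifies the test groups ("when evaluating between the test group 1 (0.25-mL QIV) and test group 2 (0.5mL-QIV"). The design table in 4.1 gives control group 1 as "Influenza Vaccine (Split Virion), Inactivated, Anflu (0.25mL, including BV") and control group 2 as "Influenza Vaccine (Split Virion), Inactivated, Anflu (0.25mL, including BY").

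The rest of SAP 6.9 (6.9.1 to 6.9.3) gives event counts, subject counts and incidences by group and in total, with Fisher's exact test between groups. It does not say whether that test is overall or pairwise. It names no rate difference and no CI for a difference.

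Protocol 2.4 supports the full dose by citing studies in which "children under 3 years old can receive full-dose vaccines to enhance immunogenicity without increasing the severity or incidence of fever or other adverse reactions".

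**The concern.** A list that a programmer will follow names the same pair twice. Taken literally, it produces one duplicate figure and drops the comparison of the 0.5 mL QIV with TIV-BY, while the 0.25 mL QIV is compared with both controls. Because these figures are the only planned AE rate differences, nothing else in the SAP supplies the lost estimate.

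The same list raises a second, independent point. It has no contrast between the two QIV doses. The trial randomizes 1,100 children to each dose, SAP 6.8 estimates the between-dose GMT ratio with a 95% CI, and the protocol's rationale for the full dose refers to reactions not increasing. A reader of the report will want the size of any difference in reactions between the doses, with its uncertainty. The plan leaves that reader to subtract two tabulated rates.

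The plots also cover only the ten most frequent preferred terms. The first two safety endpoints in Protocol 7.2, adverse reactions within 0-28 and 0-7 days after each dose, therefore get no difference estimate for any pair.

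**Working it through.** **Step 1: which pairs are listed.** T1 = 0.25 mL QIV, T2 = 0.5 mL QIV, C1 = TIV-BV, C2 = TIV-BY.

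| Pair | BV GMT ratio with 95% CI (SAP 6.8) | AE incidence difference (SAP 6.9.1) |
|---|---|---|
| T1 v C1 | yes | yes |
| T1 v C2 | yes | yes |
| T2 v C1 | yes | yes, printed twice |
| T2 v C2 | yes | no |
| T1 v T2 | yes | no |

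Four contrasts are printed and three are distinct. For H1N1 and H3N2, SAP 6.8 likewise includes T1/T2 beside the two ratios against the pooled control. The safety list follows a simpler pattern, each QIV against each TIV. Correcting the repeated entry restores T2 v C2 and completes that pattern. T1 v T2 would still be absent, so the two omissions have different origins.

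**Step 2: whether another section fills the gap.** SAP 6.1.1 gives Clopper-Pearson intervals for single percentages, not for differences. SAP 6.1.5 shows the four groups as columns. SAP 6.9.1 to 6.9.3 add Fisher's exact tests. None of these gives an AE rate difference with a CI.

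**Step 3: group sizes.** The plan's figures are 914 and 457 evaluable and about 17% dropout (SAP 4.3). 914 / (1 - 0.17) = 1,101.2, rounded up to 1,102, and 457 / (1 - 0.17) = 550.6, rounded up to 551. These agree with the stated 1,100 and 550.

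**Step 4: precision of the two missing contrasts.** The documents give no AE rates, so a common rate p is assumed in both groups. Approximate 95% half-width = 1.96 × √[p(1 - p)(1/n₁ + 1/n₂)].

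At p = 0.10:

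- T2 v T1: 1.96 × √[0.09 × (1/1,100 + 1/1,100)] = 1.96 × 0.01279 = 2.51 points.
- T2 v C2: 1.96 × √[0.09 × (1/1,100 + 1/550)] = 1.96 × 0.01567 = 3.07 points.

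| Assumed rate | T2 v T1 (1,100 v 1,100) | T2 v C2 (1,100 v 550) |
|---|---|---|
| 5% | ±1.82 points | ±2.23 points |
| 10% | ±2.51 points | ±3.07 points |
| 20% | ±3.34 points | ±4.09 points |

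The safety set needs only one vaccination, so full group sizes are a fair basis for dose 1. If the dose 2 set lost the full 17%, half-widths would grow by a factor of 1/√0.83 = 1.10. At equal event rates, the dose contrast is more precise than any QIV-TIV contrast on the list.

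**The case against.** The strongest reply is that this is one mistyped digit in a descriptive figure. No safety hypothesis or safety estimand depends on it. Both doses appear side by side in every safety table, and under SAP 6.1.1 each incidence carries its own CI. Fisher's exact tests cover all AEs, related AEs, severity, time windows, SAEs and AEs of special interest. The table and figure shells are a separate attachment (SAP 2.1) that is not available here and may already have the right pairs. All of this stands, and it limits the point to estimation. It does not make the printed list correct, and an operative list in the SAP should not depend on the shells to be read properly.

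The reply is also right about four stronger readings that a reader might infer:

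- **That the repeated entry is why the doses are not compared.** It explains only the missing T2 v C2.
- **That between-dose safety is a stated question of the trial.** Protocol 6.2 and SAP 3.1.2 ask for the safety of either dose, Protocol 7.2 sets incidences as the safety endpoints, and the between-dose objective is confined to SCR and GMT. Protocol 2.4 reports earlier studies as background.
- **That the plan compares the doses on benefit but not on harm.** Both doses are tabulated and enter the Fisher tests; only a difference with its CI is lacking.
- **That reactogenicity decides between the doses.** The documents contain no rule for choosing one. They test 0.5 mL and then 0.25 mL in sequence on immunogenicity.

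**Conclusion.** The repeated contrast is an error as written: the only planned AE rate differences leave out 0.5 mL QIV versus TIV-BY. It should be corrected before programming.

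The missing between-dose difference is a separate choice that contradicts nothing in the documents. It is still worth adding. The data are collected, the SAP already gives a between-dose interval for GMT, and the half-width would be about 1.8 to 3.3 points for event rates of 5% to 20%. Those rates are assumptions, and the figures rest on 1,100 children per dose and a normal approximation. They describe the precision on offer and do not measure harm done by the slip.

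No primary conclusion, alpha level or sample size changes.

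**What to change.** 1. In SAP 6.9.1, change the second T2 - C1 entry to test group 2 minus control group 2, and check the figure shells for the same slip.
2. As an improvement, add test group 2 minus test group 1 to the list.
3. Report risk differences with Miettinen-Nurminen 95% CIs, the method SAP 6.8 already uses for SCR, at least for adverse reactions within 0-7 and 0-28 days after each dose.
4. State whether the Fisher tests in SAP 6.9 are overall or pairwise.

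The cost is SAP wording plus a few table rows and plot lines, with no new data. Items 2 and 3 add unadjusted comparisons, which should be labelled descriptive.

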6.9.2 Serious Adverse Event

This trial mainly conducted statistical analysis on SAEs that occurred after the first dose of vaccination, including those that occurred within 6 months from the first dose of vaccination to the full course of vaccination.

The number of events, number of subjects, and incidence rates of the following types of serious adverse events will be calculated, respectively, by total and for each group. Fisher's exact test will be used to test the differences between groups.

The number, number of cases and incidence of the following SAEs will be calculated by each group and the total. Fisher's exact test will be used to statistically test the differences between groups:

- All SAEs.
- SAEs related to the investigational vaccine.
- SAEs unrelated to the investigational vaccine.

List all SAEs.

6.9.3 Adverse Events of Special Interest

This trial mainly conducted statistical analysis on AESIs that occurred after the first dose of vaccination, including events observed from the first dose until 6 months after the full vaccination. (including GBS, seizure, encephalitis, myelitis, neuritis, Bell's palsy, vasculitis, and thrombocytopenia).

The number of event, number of subjects, and incidence of the following AESIs will be calculated by each group and the total. Fisher's exact test will be used to statistically test the differences between groups:

- All AESIs.
- AESIs related to the investigational vaccine.
- AESIs unrelated to the investigational vaccine.

List all AESIs.

6.10 Handling of Missing Data

In mFAS and FAS set analyses, for missing data in the primary estimand under the assumption of Missing at Random, the Multiple Imputation method will be applied to handle missing data before non-inferiority assessment. The imputation will be performed 10 times, with the random seed set to seed=111222333.

For each imputed complete dataset, the following endpoints will be calculated at 28d post-total vaccination for each serotype:

- SCR
- SPR
- GMT (Geometric Mean Titer)
- GMI (Geometric Mean Increase)

The results from all imputed datasets will then be pooled using Rubin's rules to obtain pooled estimates for SCRs, SPRs, GMTs, and GMIs.

Additionally, for the primary estimand in the mFAS analysis set, sensitivity analyses will be conducted under the assumption of Missing Not at Random to evaluate the robustness of the results.

The following methods will be applied:

- TPA (Tipping Point Analysis) method
- δ -adjusted J2R (Jump to Reference) method

Sensitivity Analysis 1: To evaluate the impact of missing values on the primary estimand, TPA will be used for the sensitivity analysis.

- ✓ For the continuous variable, HI antibody, the TPA method will gradually adjust the possible values of the missing data of HI antibody titers of each serotype after logarithmic conversion, 28d post-total vaccination in each group, to find the critical point that reverses the conclusion of GMT analysis. Among them, the smaller the absolute value of the critical point is, the less impact the missing data has on the trial conclusion, and the better the robustness of the trial conclusion is. The Rubin method will be adopted to combine the analysis results of the datasets after each imputation, and the GMT and its 95% confidence interval of each group, as well as the corrected GMT ratio and its 95% confidence interval between each pair of groups (test group 1 / pooled control group, test group 2 / pooled control group) will be obtained through inverse logarithmic transformation. Among them, the number of seeds for multiple imputation will be taken as seed=111222333, and impute 10 times each time.
- ✓ For the categorical variable, SCR, let the number of subjects with missing HI antibody titers after 28d post-total vaccination in test group 1 that seroconverted in all analysis sets after multiple imputation in main analysis be denoted as n1, and the number of subjects with missing HI antibody titers 28d post-total vaccination in the pooled control group that did not seroconvert in all analysis sets after multiple imputation in main analysis be denoted as n2. The critical point analysis method will sequentially reverse the seroconverted subjects in test group 1 from 0, 1, 2, ..., ni (i = 1, 2) to non-seroconverted, and reverse the non-seroconverted subjects in the pooled control group to seroconverted, to find the critical point that reverses the conclusion of the SCR analysis. The Rubin method will be used to combine the analysis results of each imputed dataset to obtain the pooled SCR, the rate difference between each pair of groups, and their 95% confidence intervals. The seed number for multiple imputations is set as seed = 111222333, and each imputation is performed 10 times. If the confidence interval of the pooled rate or rate difference cannot be estimated, the Bootstrap method is used to estimate the rate or rate difference and their 95% confidence intervals. Bootstrap will perform 1000 times of sampling with replacement, with the seed number set as seed = 111.

In addition, a critical point analysis plot will be drawn to provide a visual basis for result determination.

Using the same method to conduct a sensitivity analysis for test group 2 and the pooled control group.

Sensitivity Analysis 2: To evaluate the impact of missing values on the primary estimand, the δ -adjusted J2R method will be used for sensitivity analysis.

- ✓ For the continuous variable, HI antibody, multiple imputation based on the distribution $N(\bar{X} - 0.176, S_1^2)$ will be performed for missing data of HI antibody titers of each serotype after logarithmic conversion, 28d post-total vaccination in test group 1. Multiple imputation based on the distribution $N(\bar{X}, S_2^2)$ will be performed for missing data of HI antibody titers of each serotype after logarithmic conversion, 28d post-total vaccination in the pooled control group. Here, \bar{X} represents the mean of non-missing log-transformed 28d post-total vaccination HI antibody titers calculated from the pooled control group, S_1 is the standard deviation is calculated from non-missing data in test group 1, and S_2 is the standard deviation is calculated from non-missing data in the pooled control group. The Rubin method will be adopted to combine the analysis results of the datasets after each imputation, and the GMT and its 95% confidence interval of each group, as well as the corrected GMT ratio and its 95% confidence interval between each pair of groups (test group 1 / pooled control group) will be obtained through inverse logarithmic transformation. Among them, the number of seeds for multiple imputation will be taken as seed=111222444, and impute 10 times each time.
- ✓ For the categorical variable, SCR, multiple imputation will be performed based on the Bernoulli(p_1 -0.1) distribution, where p_1 is the SCR calculated from non-missing data in the pooled control group. The Rubin method will be used to combine the analysis results of each imputed dataset to obtain the pooled SCR, the rate difference between each pair of groups, and their 95% confidence intervals. The seed number for multiple imputations is set as seed = 111222555, and each imputation is performed 10 times. If the confidence interval of the pooled rate or rate difference cannot be estimated, the Bootstrap method is used to estimate the rate or rate difference and their 95% confidence intervals. Bootstrap will perform 1000 times of sampling with replacement, with the seed number set as seed = 222.

[figure not shown]
Using the same method to conduct a sensitivity analysis for test group 2 and the pooled control group.

The same method as mentioned above will be used to conduct a sensitivity analysis for the non-inferiority comparison between the BV type and BY type test groups and the control group.

This trial will no longer process the missing data in other immunogenicity endpoints and safety endpoints.

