Using the antibody GMT 28 days after vaccination as the outcome measure, the non-inferiority margin is $\geq 2/3$ of the 95%CI lower limit of GMT ratio between the test group and the control group, and the non-inferiority margin after logarithmic conversion is $\Delta=-0.176$. The test level is taken as one-sided $\alpha=0.025$, and the power of a certain serotype GMT for non-inferiority comparison is taken as $1-\beta2/4=1-0.04/4=99\%$, and the standard deviation after logarithmic transformation is taken as $\sigma = 0.7$ with

reference to the previous research results. When comparing the non-inferiority of BY or BV, NT:NC=2:1, and PASS software is used to calculate the sample size, the test group needs 874 samples and the control group needs 437 samples. When the non-inferiority test of H1N1 or H3N2 type is carried out, two control groups are pooled. The sample size ratio of the test group and the pooled control group is 1:1, and the test group and the pooled control group need 582 participants each.

When the SCR and GMT of the test group reach the hypothesis of non-inferiority, the absolute criteria of the SCR and seroprotection rate (SPR) of the test group are further hypothesized for test. The trial requires that the SCR and SPR of the four strains of immune antibodies reach the absolute criteria, and the total power of the trial is 80%, so the power of each test is $1 - (0.2/8) = 0.975$.

(3) Calculation of sample size with the absolute criteria of SCR:

Assuming that the SCR after vaccination is 65%, the test level is one-sided $\alpha=0.025$, the lower limit of the confidence interval of the SCR should be greater than 30%, and the power of each test is 97.5%. The sample size is calculated by PASS software, and the test group needs 28 samples.

(4) Calculation of sample size with the absolute criteria of SPR:

Assuming that the SCR after vaccination is 75%, the test level is one-sided $\alpha=0.025$, the lower limit of the confidence interval of the SPR should be greater than 60%, and the power of each test is 97.5%. The sample size is calculated by PASS software, and the test group needs 146 samples.

In consideration of the above the maximum sample size and the dropout rate of about 17%, the sample size of each test group is 1,100, and the sample size of each control group is 550, with a total sample size of 3,300.

5 Analysis Sets

(1) Immunogenicity Analysis Set

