Immunogenicity analyses will be performed primarily based on the Per Protocol Set (PPS), with complementary analyses based on the Full Analysis Set (FAS) and the modified Full Analysis Set (mFAS).

➤ Modified Full Analysis Set (mFAS)

The subject population defined according to intention-to-treat (ITT) principles includes all randomized subjects who have completed the full course of vaccinations, completed blood collection prior to vaccination, and had an effective antibody titer value.

➤ Full Analysis Set (FAS)

The subject population defined according to intention-to-treat (ITT) principles includes all randomized subjects who have completed at least one vaccination, completed blood collection prior to vaccination, and had an effective antibody titer value. Subjects who are administered the vaccine erroneously will be included in the immunogenicity analysis as randomized.

➤ Per Protocol Set (PPS)

It will be a subset of FAS and included all subjects who met the inclusion criteria and did not meet

exclusion criteria, randomized and received full-course vaccination, had a blood sample collected within the time window required by the protocol, and obtained blood sample test results before/after immunization. The subjects who met the following conditions will be excluded from PPS:

- 1) Those who have significant protocol deviations (affecting immunogenicity evaluation).
- 2) Those who are vaccinated with the wrong vaccine.
- 3) Subject received a protocol-prohibited medication/vaccine.
 - Other investigational or unregistered products (drugs or vaccines) that are not investigational vaccines.
 - Use of influenza vaccines other than investigational vaccines.
 - Long-term use (for more than 14 consecutive days) of immunosuppressive or other immunomodulatory drugs (inhaled or topical steroids are allowed).
 - Immunoglobulins or blood products.
- 4) Other conditions that may affect the evaluation of immunogenicity of 28 days after full-course vaccination.

Define the above mFAS, FAS, and PPS for each type (including H1N1, H3N2, BV, and BY), respectively.

(2) Safety Set (SS)

The safety set includes all randomized subjects who have received at least one vaccination. In the safety evaluation, subjects with vaccination erroneously will be included in the statistical analysis based on the actual vaccine groups they received, according to the principle of ASaT (All Subjects as Treated).

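### SAP 6.10 states the reading rule for the GMT tipping-point analysis backwards: it calls a smaller critical point more robust, when it means the conclusion is easier to overturn

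*SAP*

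**What the plan says.** SAP 6.10 (Handling of Missing Data) plans two analyses under missing-not-at-random assumptions, both on the mFAS. The first is a tipping-point analysis. For the continuous endpoint it adjusts the missing log titres at 28 days after the second dose, for every serotype and in each group, "to find the critical point that reverses the conclusion of GMT analysis". The next sentence tells the reader how to interpret the answer: "the smaller the absolute value of the critical point is, the less impact the missing data has on the trial conclusion". It goes on to equate a smaller critical point with a more robust result.

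The parallel analysis for seroconversion reverses imputed responders and non-responders one at a time, "to find the critical point that reverses the conclusion of the SCR analysis". It gives no rule for reading the count. SAP 6.10 also says that "a critical point analysis plot will be drawn to provide a visual basis for result determination".

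The GMT text covers each serotype. The end of SAP 6.10 adds that the same method "will be used to conduct a sensitivity analysis for the non-inferiority comparison between the BV type and BY type test groups" and their controls. No other part of the SAP restates or corrects the rule, and Protocol 9.11 refers to the SAP for all statistics.

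**The concern.** The two consecutive sentences contradict each other. If the critical point is the adjustment that flips the conclusion, its size measures how far the missing values must depart from the imputation model before the answer changes. A critical point near zero means that a slight departure is enough, so the missing data matter a great deal. The SAP attaches the opposite meaning to it.

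This sentence is the only pre-specified guide to reading an analysis whose stated purpose is to judge robustness. A statistician who followed it would report a fragile GMT result as robust and a robust one as fragile. Because more missing data also pulls the critical point towards zero, the rule would credit missing data with less impact as their share grows.

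**Working it through.** The direction follows from the definition alone. The arithmetic below shows it on the plan's own inputs.

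**Inputs from SAP 4.3 (GMT).** For BV and BY, "the test group needs 874 samples and the control group needs 437 samples". The SD is 0.7 on the log10 scale, the margin is log10(2/3) = -0.1761, one-sided alpha is 0.025, and power per serotype is 99%.

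**Reproducing the plan's figures.** (0.7 × (1.960 + 2.326) / 0.176)² = 290.6.
- For 2:1 allocation, the control group needs 1.5 × 290.6, which rounds up to 436, and the test group 872 (plan: 437 and 874).
- For 1:1 allocation, each group needs 2 × 290.6, which rounds up to 582 (plan: 582).

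The SD and margin are therefore the ones the plan used.

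**Assumptions.** The documents give no missing share for the mFAS and no observed ratio. I take 5%, 10% and 17% missing. The last is the plan's dropout rate and serves as an upper value, because the mFAS requires the full vaccination course. I take two observed log10 differences: 0, and -0.08 (a GMT ratio of 0.83).

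**Standard error.** SE = 0.7 × √(1/874 + 1/437) = 0.0410, and 1.96 × SE = 0.0804. The A-strain sizes of 582 vs 582 give the same SE.

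**Lower 95% limits before any shift.** They are -0.080 for difference 0 and -0.160 for difference -0.08. Both lie above -0.1761, so non-inferiority holds in both.

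**Critical point.** Shifting a share f of the test arm down by δ lowers the difference by fδ. With the SE held fixed, the conclusion flips at δ = (0.1761 - |lower limit|) / f. This is 0.0957 / f for difference 0 and 0.0157 / f for difference -0.08.

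| Missing share | Difference 0 | Difference -0.08 |
|---|---|---|
| 5% | 1.91 | 0.31 |
| 10% | 0.96 | 0.16 |
| 17% | 0.56 | 0.09 |

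**Refinement 1: variance that grows with the shift.** Moving part of one arm adds f(1 - f)δ² to that arm's variance, so the conclusion tips sooner. With a pooled within-group variance, the difference-0 column becomes 1.76, 0.92 and 0.55. The other column stays at 0.31, 0.16 and 0.09.

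**Refinement 2: Rubin variance for 10 imputations.** T = W + 1.1 × B, where W = 0.49 × (1/874 + 1/437) and B is the extra variance when a share f is missing in both arms. This gives SE = 0.0422, 0.0434 and 0.0454. With no growth in variance, the critical points are 1.87, 0.91 and 0.51 for difference 0, and 0.27, 0.11 and 0.04 for difference -0.08.

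**Cross-check at the planned arm sizes.** With 1,100 vs 550, 10% missing and a variance that grows with the shift, the critical points in absolute value are 0.09, 0.30, 0.54, 0.98 and 1.38 for GMT ratios of 0.81, 0.85, 0.90, 1.00 and 1.10. A multiple-imputation simulation on a grid of 0.05 gave 0.15, 0.30, 0.65, 1.00 and 1.40.

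**Reading.** In every setting the critical point shrinks as the result approaches the margin and as more data are missing. The SAP rule ranks these cases in exactly the reverse order.

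**The case against.** The strongest objection concerns weight. Immunogenicity rests primarily on the PPS (SAP 5), and the tipping-point analysis is one of two sensitivity analyses on the mFAS. The other, the δ-adjusted jump-to-reference analysis, does not use this rule. None of the criteria in SAP 6.8 refers to a critical point. The computed values and the plot would be right, and an informed reader could interpret them correctly. The sentence may be a one-word slip. All of this stands, and it limits the consequence to the wording of a report.

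A second objection is that the illustration is approximate. It leaves out the baseline covariate of the planned ANCOVA, and its main table uses the minimum evaluable sizes and a fixed SE. That also stands: the fixed-SE values are up to about 8% too high (1.91 against 1.76). The ordering does not change, and the planned arm sizes give the same picture.

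Two alternative readings do not rescue the text. If the critical point were the imputed titre itself, a low value might suggest robustness in the test arm. But the SAP adjusts values in each group, the direction would be opposite in the control arm, and an absolute value fits a signed shift. If the starting conclusion were that non-inferiority was not shown, a firmer failure would still need a larger shift to reverse, so the rule would remain backwards.

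It is also fair to say that the missing reading rule for SCR is not an error, since counting reversals upward from zero largely explains itself.

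**Conclusion.** The concern holds. The reading rule for the GMT tipping-point analysis is inverted as written, nothing elsewhere corrects it, and it applies to all four strains. It should be fixed, but its reach is narrow: only the pre-specified interpretation of one sensitivity analysis is wrong.

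The conclusion about direction needs no assumption beyond the SAP's own definition of the critical point. The sizes quoted are illustrations that rest on assumed missing shares and observed differences. They are not predictions for this trial.

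**What to change.** Replace the sentence in SAP 6.10, Sensitivity Analysis 1, with wording such as:

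> A larger absolute critical point means that a larger departure from the missing-at-random imputation is needed to reverse the conclusion. The missing data then have less influence, and the conclusion is more robust.

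Optionally, add the matching line for SCR: the more subjects that must be reversed before the conclusion changes, the more robust it is. No plausibility cut-off is needed for this correction; if one is wanted, it needs its own justification.

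The cost is one corrected sentence and, if chosen, one added sentence. Data, programming and sample size are untouched. If results have already been written up, check that the text on robustness of the GMT findings did not follow the inverted rule.
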